6.2.3.8. Counting rules for combining solicited and unsolicited adverse events

For output combining solicited and unsolicited adverse events, all serious adverse events will be considered systemic events since the administration site flag is not included in the expedited adverse event CRF pages. Unsolicited adverse events with missing administration site flag will also be considered systemic.

Solicited events will be coded by MedDRA as per the following codes:

Solicited event	Lower level term code	Corresponding Lower level term decode
Pain	10022086	Injection site pain
Erythema	10022061	Injection site erythema
Swelling	10053425	Injection site swelling
Fever	10016558	Fever
Headache	10019211	Headache
Fatigue	10016256	Fatigue
Myalgia	10028411	Myalgia
Arthralgia	10003239	Arthralgia

The latest available MedDRA version will be used for coding

Multiple events with the same preferred term which start on the same day are counted as only one occurrence.

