- 3 (severe) = An AE which prevents normal, everyday activities. In adults, such an AE would, for example, prevent attendance at work and would necessitate the administration of corrective therapy.

An AE that is assessed as Grade 3 (severe) should not be confused with an SAE. Grade 3 is a category used for rating the intensity of an event; and both AEs and SAEs can be assessed as Grade 3. An event is defined as 'serious' when it meets 1 of the pre-defined outcomes as described in the Section [10.3.2](#).

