4.3.2. Safety analysis

The safety analysis will be performed on the ES as follows:

- The number and percentage of participants and doses with at least one administration site event AE (solicited and unsolicited), with at least one systemic AE (solicited and unsolicited) and with any AE during the 4-day (i.e. the day of vaccination and 3 subsequent days) and 30-day (i.e. the day of vaccination and 29 subsequent days) follow-up period will be tabulated with exact 95% confidence interval (CI) after each dose and overall. The same computations will be done for Grade 3 AEs, for Grade 3 non-serious AEs and for AEs resulting in a medically attended visit.

These analyses will present all solicited and unsolicited AEs, including SAEs and pIMDs (unless otherwise specified).

The above analysis will also be performed for the solicited symptoms only during the 4-day (i.e. the day of vaccination and 3 subsequent days) follow-up period.

- The number and percentage of participants reporting each individual solicited administration site AE (any grade, Grade 3 and resulting in medically attended visit) and solicited systemic AE (any grade, Grade 3 and resulting in medically attended visit) during the 4-day follow-up period (i.e. the day of vaccination and 3 subsequent days) will be tabulated for each group after each dose and overall. The percentage of doses followed by each individual solicited administration site AE (any grade, Grade 3 and resulting in medically attended visit) and solicited systemic AE (any grade, Grade 3 and resulting in medically attended visit) during the 4-day follow-up period (i.e. the day of vaccination and 3 subsequent days) will be tabulated, with exact 95% CI.
- For fever, the number and percentage of participants reporting fever by half degree (°C) cumulative increments during the 4-day follow-up period (i.e. the day of vaccination and 3 subsequent days) will be tabulated for each group after each dose and overall.
- The percentage of participants with each solicited administration site event and solicited systemic event (any grade and Grade 3) will be represented graphically for each group after each dose.
- The number of days with solicited events reported during the 4-day follow-up period will be tabulated for each individual solicited event using descriptive statistics (mean, minimum, Q1, median, Q3, maximum). The same computations will be done for Grade 3 solicited events.

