6.2.3.9. Counting rules for occurrences of solicited events

When the occurrences of solicited events are summarized, each event recorded as having occurred during a specific period will be counted as only one occurrence regardless of the number of days on which it occurs. Also, in the case of co-administered study interventions, an administration site event recorded for a participant following multiple study interventions will be counted as only one occurrence.

Table 4 Intensity grading scale for solicited events

Event	Intensity Grade	Parameter
Pain at administration site	0	None
	1	Mild: Any pain neither interfering with nor preventing normal everyday activities.
	2	Moderate: Painful when limb is moved and interferes with everyday activities.
	3	Severe: Significant pain at rest. Prevents normal everyday activities.
Erythema at administration site		Greatest surface diameter in mm
Swelling at administration site		Greatest surface diameter in mm
Temperature*		Temperature in °C.
Headache	0	None
	1	Mild: Headache that is easily tolerated
	2	Moderate: Headache that interferes with normal activity
	3	Severe: Headache that prevents normal activity
Fatigue	0	None
	1	Mild: Fatigue that is easily tolerated
	2	Moderate: Fatigue that interferes with normal activity
	3	Severe: Fatigue that prevents normal activity
Myalgia	0	None
	1	Mild: Myalgia that is easily tolerated
	2	Moderate: Myalgia that interferes with normal activity
	3	Severe: Myalgia that prevents normal activity
Arthralgia	0	None
	1	Mild: Arthralgia that is easily tolerated
	2	Moderate: Arthralgia that interferes with normal activity
	3	Severe: Arthralgia that prevents normal activity

The route for measuring temperature can be oral or axillary. Fever is defined as temperature $\geq 38.0^{\circ}\text{C}$ regardless of the location of measurement.

The maximum intensity of local injection site erythema/swelling and fever will be scored at GSK as follows:

	Erythema/swelling	Fever
0:	$\leq 20\text{mm}$	$< 38.0^{\circ}\text{C}$
1:	$> 20 - \leq 50\text{mm}$	$\geq 38.0^{\circ}\text{C} - \leq 38.5^{\circ}\text{C}$
2:	$> 50 - \leq 100\text{mm}$	$> 38.5^{\circ}\text{C} - \leq 39.0^{\circ}\text{C}$
3:	$> 100\text{mm}$	$> 39.0^{\circ}\text{C}$

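### Serious injection-site events, and unsolicited AEs with no site flag, are counted as systemic in the combined AE tables

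*SAP*

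**What the plan says.** SAP 6.2.3.8 sets counting rules whose scope is given in its opening words: "For output combining solicited and unsolicited adverse events". Within that scope, "all serious adverse events will be considered systemic events since the administration site flag is not included in the expedited adverse event CRF pages". It adds: "Unsolicited adverse events with missing administration site flag will also be considered systemic".

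The outputs concerned are in SAP 4.3.2. The first safety analysis counts participants and doses "with at least one administration site event AE (solicited and unsolicited), with at least one systemic AE (solicited and unsolicited", and also those with any AE, over the 4-day and 30-day periods. SAEs are part of it: "These analyses will present all solicited and unsolicited AEs, including SAEs and pIMDs". The tables are then repeated: "The same computations will be done for Grade 3 AEs, for Grade 3 non-serious AEs and for AEs resulting in a medically attended visit".

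The same section classifies SAEs and unsolicited AEs by MedDRA System Organ Class, High Level Term and Preferred Term. SAP 6.2.3.8 itself maps solicited pain, erythema and swelling to injection-site terms.

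**The concern.** A table row for administration-site AEs should be able to show a serious one. Under this rule it cannot. If a participant is admitted to hospital with an infection at the injection site, the event counts as systemic because of the form it was reported on. An empty serious-local category would then reflect the counting rule and not the data, and a reader of the table alone could not tell the difference.

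The reason given is a data-collection gap: the expedited reporting pages have no site flag. That gap does not force the rule, because the planned MedDRA coding already carries site information for every event whose coded term names the site. The handling of a missing flag also differs from the SAP's practice elsewhere. SAP 6.2.3.10 displays missing severity, relationship and outcome of unsolicited AEs as unknown, whereas a missing site flag is always resolved towards systemic.

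At stake is the local/systemic split within the secondary safety and reactogenicity objective. The Co-Ad group receives two injections at one visit and the Control group one at each of two visits, so local tolerability is a natural thing to compare.

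**Working it through.** The plan states no rate or count for serious injection-site events, so there is no figure to reproduce. The check is a reading of the rules side by side, followed by a bound on the effect.

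**1. Does the rule have any effect?** Yes. It covers combined outputs (SAP 6.2.3.8), and the combined outputs in SAP 4.3.2 have site and systemic rows and include SAEs.

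**2. Which rows become redundant?** Let S be the participants with a Grade 3 non-serious site AE, and T those with a serious Grade 3 event counted as a site AE. The Grade 3 site row is S ∪ T and the Grade 3 non-serious site row is S. The rule makes T empty, so the two rows are equal whatever the data. This is the literal reading. The documents do not say whether a solicited site event that meets an SAE criterion also keeps its diary record and counts as local through that record.

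**3. Does the rule act on severity?** No. Protocol 10.3.8.1 states: "An AE that is assessed as Grade 3 (severe) should not be confused with an SAE". Grade 3 pain at the site is defined by intensity alone ("Severe: Significant pain at rest. Prevents normal everyday activities"), and Grade 3 erythema or swelling by a diameter above 100 mm. A flagged, non-serious Grade 3 site reaction stays in the administration-site rows.

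**4. How large is the shift?** The input is 514 participants per group, the target enrolment in Protocol 9.2 and SAP 5; the actual Exposed Set may differ.

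- One affected participant: 1/514 = 0.19 percentage points.
- Three affected participants: 3/514 = 0.58 points.

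These are maxima. The rows count participants with at least one event, so someone with a non-serious site event in the same period, such as injection-site pain, still counts as local and the shift is zero.

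For illustration, take an assumed rate p of serious site events per participant. Expected affected participants per group = 514 × p, and the chance of at least one = 1 − (1 − p)^514. All values of p are assumptions.

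| Assumed p | Expected per group | Chance of at least one | Largest fall in site row |
|---|---|---|---|
| 0.1% | 0.5 | 0.40 | 0.1 points |
| 0.5% | 2.6 | 0.92 | 0.5 points |
| 1% | 5.1 | 0.99 | 1.0 points |

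The relative effect is larger in the Grade 3 row, where the base is smaller. With an assumed 2% Grade 3 site rate, of which 0.1 to 0.5 points are serious, the row keeps (2 − 0.1)/2 = 95% down to (2 − 0.5)/2 = 75% of its participants.

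**5. Where else do the events appear?** They appear in the systemic and any-AE rows of the same tables, in the SAE table by System Organ Class, High Level Term and Preferred Term, and in the listing of all SAEs (SAP 4.3.2). The solicited-only version of the analysis and the tables of individual solicited events fall outside the rule's stated scope.

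**The case against.** The strongest reply is that this is a declared convention with a stated reason, that it treats both groups alike, and that it hides nothing. Every serious event is tabulated under its own preferred term and listed individually. The safety endpoints named in the protocol are solicited events, unsolicited AEs, SAEs and pIMDs; none of them is a combined local/systemic split. All of this stands, and it is why the point is minor.

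Three stronger readings are tempting, and the documents do not support them.

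- A reader might infer that the most severe injection-site reactions are taken out of the local rows. The SAE rule acts on seriousness, and the protocol separates that from Grade 3.
- A reader might infer that serious local events are lost from the report. They are only placed in a different row of one family of tables.
- A reader might infer that the rule favours co-administration. It applies identically to both groups, Control participants also receive two injections over the study, and nothing in the documents shows a between-group bias.

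It can also be objected that MedDRA coding may not rescue every case. The SAP gives codes only for the eight solicited events, so the documents do not show that an infection or abscess at the site would fall under a site-reaction High Level Term. That is fair, and it argues for an explicit list of preferred terms over a hierarchy criterion. It does not justify a rule under which no serious event can ever be local.

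**Conclusion.** The point holds as a minor correction. In the combined AE tables, serious injection-site events and unflagged unsolicited AEs are counted as systemic by rule, so the administration-site rows cannot show a serious local reaction. On a literal reading, the Grade 3 and Grade 3 non-serious site rows cannot differ.

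The size is at most 0.19 percentage points per affected participant with 514 per group, and often less, because another site event in the same participant removes the shift. How many participants would be affected is unknown: the documents give no rate, and those in the table above are assumptions. No primary endpoint, named safety endpoint or solicited-only table changes. The practical risk is that an entry of no serious local events in a summary table is taken as a finding when it follows from the counting rule.

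**What to change.** In SAP 6.2.3.8:

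1. Classify an SAE, or an unsolicited AE with a missing site flag, as an administration-site event when its MedDRA preferred term is on a pre-specified list of injection-, administration- or vaccination-site terms, and as systemic otherwise.
2. State how a solicited site event that becomes serious is counted, and whether its diary record still contributes to the administration-site row.
3. Footnote the combined tables with the classification rule and the number of site-coded SAEs per group.

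If the present rule is kept, item 3 alone is the minimum, since it tells the reader what the site row cannot show.

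The cost is a short term list to agree before the analysis, one derivation using codes already planned, and a footnote. No new data are needed. The limitation is that events whose coded term does not name the site would still default to systemic.

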6.2.3.9. Counting rules for occurrences of solicited events

When the occurrences of solicited events are summarized, each event recorded as having occurred during a specific period will be counted as only one occurrence regardless of the number of days on which it occurs. Also, in the case of co-administered study interventions, an administration site event recorded for a participant following multiple study interventions will be counted as only one occurrence.

Table 4 Intensity grading scale for solicited events

Event	Intensity Grade	Parameter
Pain at administration site	0	None
	1	Mild: Any pain neither interfering with nor preventing normal everyday activities.
	2	Moderate: Painful when limb is moved and interferes with everyday activities.
	3	Severe: Significant pain at rest. Prevents normal everyday activities.
Erythema at administration site		Greatest surface diameter in mm
Swelling at administration site		Greatest surface diameter in mm
Temperature*		Temperature in °C.
Headache	0	None
	1	Mild: Headache that is easily tolerated
	2	Moderate: Headache that interferes with normal activity
	3	Severe: Headache that prevents normal activity
Fatigue	0	None
	1	Mild: Fatigue that is easily tolerated
	2	Moderate: Fatigue that interferes with normal activity
	3	Severe: Fatigue that prevents normal activity
Myalgia	0	None
	1	Mild: Myalgia that is easily tolerated
	2	Moderate: Myalgia that interferes with normal activity
	3	Severe: Myalgia that prevents normal activity
Arthralgia	0	None
	1	Mild: Arthralgia that is easily tolerated
	2	Moderate: Arthralgia that interferes with normal activity
	3	Severe: Arthralgia that prevents normal activity

The route for measuring temperature can be oral or axillary. Fever is defined as temperature $\geq 38.0^{\circ}\text{C}$ regardless of the location of measurement.

The maximum intensity of local injection site erythema/swelling and fever will be scored at GSK as follows:

	Erythema/swelling	Fever
0:	$\leq 20\text{mm}$	$< 38.0^{\circ}\text{C}$
1:	$> 20 - \leq 50\text{mm}$	$\geq 38.0^{\circ}\text{C} - \leq 38.5^{\circ}\text{C}$
2:	$> 50 - \leq 100\text{mm}$	$> 38.5^{\circ}\text{C} - \leq 39.0^{\circ}\text{C}$
3:	$> 100\text{mm}$	$> 39.0^{\circ}\text{C}$

6.2.3.10. Counting rules for occurrence of unsolicited adverse events

Unsolicited AE summaries will include SAEs and pIMDs unless specified otherwise.

As per CDISC Vaccines Therapeutic Area guide, the solicited events which continue beyond the observation period are stored in the Adverse Events (AE) domain but will not contribute to the summaries of unsolicited AEs.

Missing severity, relationship with study vaccine, and outcome of unsolicited adverse events will not be replaced and will appear as 'UNKNOWN' when displayed in a statistical output.

6.2.4. Display of decimals

6.2.4.1. Percentages

Percentages and their corresponding confidence limits will be displayed with one decimal except for 100% in which case no decimal will be displayed.

6.2.4.2. Differences in percentages

Differences in percentages and their corresponding confidence limits will be displayed with two decimals.

6.2.4.3. Demographic/baseline characteristics statistics

The mean, median, and standard deviation for continuous baseline characteristics (age at first vaccination pre-dose body temperature) will be presented with one decimal.

The minimum and maximum values and quartile values (if required) will be presented with the same number of decimals as the observed values.

The maximum and minimum of transformed body temperatures will be displayed with one decimal.

6.2.4.4. Serological summary statistics

For each assay, geometric mean titers (GMT) **cci** and their confidence limits will be presented with one decimal, as well as **GMT_{cci}** fold increase from pre-dose.

GMT **cci** group ratios and their confidence limits will be displayed with 2 decimals regardless of the actual values.

